10.7. Appendix 7: Premature Withdrawals & Handling of Missing Data

10.7.1. Premature Withdrawals

Element	Reporting Detail
General	
 Subject study completion (i.e. completion of all study visits or withdraw prematurely from the study) was detailed in the study protocol. Withdrawn subjects will not be replaced in the study. All available data from subjects who were withdrawn from the study will be listed and all available planned data will be included in data displays (e.g. summary tables) unless otherwise specified.
Pre-Screen, Screen and Run-in Failures	
Pre-screen failures, screening failures and run-in failures will be defined as follows:
 
 Subjects will be assigned a subject number at the time the informed consent is signed (Pre-screen Visit). Subjects who are assigned a subject number but do not have a Visit 1 (screening) procedure will be considered pre-screen failures. Those subjects that complete at least one Visit 1 (Screening) procedure but do not enter the run-in period will be considered screen failures. Those subjects that enter the run-in period but are not subsequently dosed will be considered run-in failures.

10.7.2. Handling of Missing Data

Element	Reporting Detail
General	
 Missing data occurs when any requested data is not provided. These data will be indicated by the use of a "blank" in subject listing displays. Unless all data for a specific visit are missing in which case the data is excluded from the listing. Answers such as "Not applicable" and "Not evaluable" are not considered to be missing data and should not be displayed as missing. PK concentrations reported as Not Quantified (NQ)/Below the Lower Limit of Quantification (BQL) will be handled as per standard GSK practice. Below the limit of quantification (BLQ) is not missing data and must be displayed as such and included in all listings and summaries

Element	Reporting Detail
	
 If a blood eosinophil count of zero is reported, it will be imputed with half of the lowest possible blood eosinophil count, where applicable, prior to log transforming the data (Note: this imputation has typically been $0.5 * 0.01$ GI/L = 0.005 GI/L for previous mepolizumab studies). The ACQ-7 score will be considered as missing if <6 items of the questionnaire are completed at a visit. ACQ-7 Responder/Non-responder category will be missing if the overall ACQ-7 score is missing. The ACQ-5 score will be considered as missing if <4 items of the questionnaire are completed at a visit. ACQ-5 Responder/Non-responder category will be missing if the overall ACQ-5 score is missing. Missing values will not be imputed for any of the other endpoints.
Outliers	
 Any subjects excluded from the summaries and/or statistical analyses will be documented along with the reason for exclusion in the clinical study report.
Sensitivity analysis	
 No sensitivity analyses are planned for this study. However as detailed in Section 7, exploratory sensitivity analyses may be considered if there are protocol deviations that may potentially affect the PK and/or PD endpoints. If any sensitivity analyses are performed the details will be documented in the clinical study report.

10.7.2.1. Handling of Missing and Partial Dates

Element	Reporting Detail
General	
 The eCRF allows for the possibility of partial dates (i.e. only month and year) to be recorded for event start and end dates; that is, the day of the month may be missing. Partial dates will be displayed as captured in subject listing displays.
Concomitant Medications	
 Partial dates for any concomitant medications recorded in the CRF will be imputed using the following convention: 
 If the partial date is a start date, a '01' will be used for the day and 'Jan' will be used for the month If the partial date is a stop date, a '28/29/30/31' will be used for the day (dependent on the month and year) and 'Dec' will be used for the month. The recorded partial date will be displayed in listings.
AEs	
 Any partial dates for adverse events and exacerbations will be raised to data management. If the full date cannot be ascertained, the following assumptions will be made: 
 If the partial date is a start date, a '01' will be used for the day and 'Jan' will be used for the month. However, if these results in a date prior to the first dose of mepolizumab and the event could possibly have occurred during treatment from the partial information, then the first dose of mepolizumab date will be assumed to be the start date. The AE will then be considered to start on-treatment (worst case) as per Appendix 4: Treatment Phases. If the partial date is a stop date, a '28/29/30/31' will be used for the day

Element	Reporting Detail
	
(dependent on the month and year) and 'Dec' will be used for the month.
 
 • The above conventions will also be applied when calculating the time to onset and duration of the event containing missing or partial start and end dates. • The recorded partial date will be displayed in listings. • Start or end dates which are completely missing (i.e. no year specified) will remain missing, with no imputation applied. Consequently, time to onset and duration of such events will be missing.

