10.4.2. Treatment Phases (Exacerbations)

Exacerbation data will be classified according to time of occurrence/assessment relative to the first and last dose of mepolizumab and the participation of subjects within to specific study parts (as dictated by attendance dates of specific visits).

Treatment Phase	Definition
Pre-Treatment	Exacerbation Onset Date & time < First Part A dose of mepolizumab If mepolizumab treatment is never started then all exacerbations will be classified as pre-treatment.
On-Treatment (Part A)	Subjects completing Part A: First Part A dose of mepolizumab ≤ Exacerbation Onset Date & time ≤ Visit 6 (Week 12) visit date Subjects discontinuing study treatment/withdrawing early from Part A: First Part A dose of mepolizumab ≤ Exacerbation Onset Date & time ≤ Earliest of (1) Last Part A dose of mepolizumab + 28 days or (2) Early Withdrawal visit date
Post-treatment (Part A)	Subjects completing Part A and entering Part B: Visit 6 (Week 12) visit date < Exacerbation Onset Date & time < First dose of Part B mepolizumab Subjects completing Part A and not entering Part B: Visit 6 (Week 12) visit date < Exacerbation Onset Date & time ≤ Visit 8 (Week 20) visit date Subjects discontinuing study treatment/withdrawing early from Part A: Earliest of (1) Last Part A dose of mepolizumab + 28 days or (2) Early Withdrawal visit date < Exacerbation Onset Date & time ≤ Visit 8 (Week 20) visit date
On-Treatment (Part B)	Subjects completing Part B: First Part B dose of mepolizumab ≤ Exacerbation Onset Date & time ≤ Visit 22 (Week 72) visit date Subjects discontinuing study treatment/withdrawing early from Part B: First Part B dose of mepolizumab ≤ Exacerbation Onset Date & time ≤ Earliest of (1) Last Part B dose of mepolizumab + 28 days or (2) Early Withdrawal visit date
Post-treatment (Part B)	Subjects completing Part B: Exacerbation Onset Date & time > Visit 22 (Week 72) visit date Subjects discontinuing study treatment/withdrawing early from Part B: Exacerbation Onset Date & time > Earliest of (1) Last Part B dose of mepolizumab + 28 days or (2) Early Withdrawal visit date

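### As written, the SAP's partial-date rule replaces a recorded month with January or December, and its first-dose fallback names no study part

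*SAP*

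**What the plan says.** The General row of SAP 10.7.2.1 defines the situation: "The eCRF allows for the possibility of partial dates (i.e. only month and year) to be recorded for event start and end dates". So the month is known and only the day can be absent.

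The AEs row, which also covers exacerbations, starts with a query step: "Any partial dates for adverse events and exacerbations will be raised to data management". If the query fails, the start rule is "If the partial date is a start date, a '01' will be used for the day and 'Jan' will be used for the month". The stop rule takes a month-end day, "dependent on the month and year) and 'Dec' will be used for the month". The concomitant-medication row uses the same two rules.

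The AEs row adds a fallback. If the imputed start precedes the first dose and onset during treatment is possible, "then the first dose of mepolizumab date will be assumed to be the start date". No study part is named. On use: "The above conventions will also be applied when calculating the time to onset and duration of the event".

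SAP 10.3.1 assigns spontaneous events to a study part by date. SAP 10.4.1 treats a partially dated adverse event as on-treatment unless the recorded month and year show otherwise, with a separate rule for each part. SAP 10.4.2 has no such default. For children completing Part B, an exacerbation is on-treatment when "First Part B dose of mepolizumab ≤ Exacerbation Onset Date & time ≤ Visit 22 (Week 72) visit date".

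**The concern.** In the only kind of partial date that the SAP describes, the rule tells the programmer to overwrite information that was collected. Onset moves earlier and the stop date moves later, so time to onset and duration are both distorted. For adverse events the treatment phase is protected by SAP 10.4.1. For exacerbations the phase follows the imputed date alone.

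The outputs at stake are the exacerbation counts and the time-to-first-exacerbation estimates (SAP 8.1.6 and Table 7), and time to onset in the profile tables for adverse events of special interest (SAP 8.2.1.1). With about 28 treated children planned (protocol 4.3), one misplaced exacerbation could visibly change a count.

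**Working it through.** The documents give no figure on this point, so there is none to reproduce. The check applies the rule to dates.

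**Inputs from the documents.** The Week 12 visit is day 84 after the first dose, the first Part B dose (Week 20) is day 140, and Week 72 is day 504. The phase windows are those of SAP 10.4.2. Duration is stop minus start plus 1.

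**Assumptions, not in the documents.** Visits are exactly on schedule. First doses are spread evenly over one calendar year (2016). Onsets are uniform. Every date considered lacks its day and is still unresolved after query. Unless stated otherwise, the fallback dose is the first Part A dose.

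**1. One child.** First dose 15 Mar 2016; first Part B dose 15 Mar + 140 days = 2 Aug 2016; Week 72 is 1 Aug 2017.

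| Recorded start and stop | Rule read literally | Recorded month kept |
|---|---|---|
| Oct 2016 to Oct 2016 | 1 Jan 2016, moved by the fallback to 15 Mar 2016; stop 31 Dec 2016. Onset day 1, duration 292 days, Part A on-treatment | 1 Oct to 31 Oct 2016. Onset day 201, duration 31 days, Part B on-treatment |
| Feb 2017 to Feb 2017 | 1 Jan to 31 Dec 2017. Duration 365 days, Part B on-treatment | 1 Feb to 28 Feb 2017. Duration 28 days, Part B on-treatment |
| Aug 2016 to Aug 2016, true onset 20 Aug | 15 Mar to 31 Dec 2016. Duration 292 days, Part A on-treatment | 1 Aug to 31 Aug 2016. Onset one day before the first Part B dose, so Part A post-treatment |

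The February row shows that the part is not always wrong. The August row shows an error that remains when the month is kept.

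**2. Onset and duration.** Over every first-dose date in the year and every onset from day 0 to day 504, the literal rule gives a mean onset error of 138 days (maximum 365). With the month kept it is 14 days (maximum 30). A true 10-day event with both dates partial gets a median duration of 365 days under the literal rule and 31 days with the month kept.

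**3. Study part, literal rule.** The imputed start precedes the first Part B dose whenever the onset falls in the same calendar year as that dose (unless the dose is on 1 January). If a fraction x of the year has passed at that dose, a share 1 − x of the next 365 days of onsets (days 140 to 504) falls in the same year. Averaged over x from 0 to 1 this is 1/2. The day-by-day count gives 49.9%: 36.0% in the Part A on-treatment window and 13.9% in the Part A post-treatment window.

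**4. Study part, month kept.** An onset is misplaced only if it falls in the calendar month of the first Part B dose. In a month of m days, with the dose on day d (d ≥ 2), the onsets on days d to m are imputed to the 1st, which is before the dose. That is m − d + 1 days, with mean (m − 1)/2 over all d. With m = 365/12 = 30.4, the mean is 14.7 days, and 14.7/365 = 4.0%. The day-by-day count also gives 4.0%, all in the Part A post-treatment window.

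**The case against.** The best defence is that the literal reading was not intended. A stop day that depends on the month makes no sense if the month is always December. The same section calls a date completely missing only when it has no year, which leaves year-only dates as the natural use of January and December. SAP 10.4.1 also reasons from a recorded month and year. This is persuasive on intent, and on that reading the errors in steps 2 and 3 from overwriting the month disappear. It does not rescue the text: the General row describes only month-and-year dates, and the instruction carries no condition.

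A second defence is that the Part A anchor is an inference. SAP 10.5.2.1 and 10.6.1 use the first dose of mepolizumab for the start of Part A, but the exposure rule in SAP 10.6.2 uses it within each part. This stands: the anchor is unclear, and the 4% holds only if it is the Part A dose.

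A third is that few records are exposed. Partial dates are queried first, exacerbations are assessed at every visit (protocol 7.9), and dates of all concomitant medications are collected (protocol 6.9.1). The 365-day duration needs both dates to be partial. The summaries are exploratory and descriptive, and listings show the recorded partial date. All of this stands and limits the size, although listings do not correct tables or Kaplan-Meier estimates.

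A reader might infer from step 3 that half of the Part B exacerbations would be reported in Part A. The documents do not support that. The half applies only to unresolved partial dates read literally. Also, Part A is reported from a data cut at the last child's Week 20 visit (SAP 10.3.2), and its outputs are not reproduced (SAP 3.2). A Part B event after the cut cannot enter a Part A table; it would simply be missing from the Part B summary.

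**Conclusion.** The rule is wrong as written, with limited effect. Followed literally, it discards a recorded month, gives early onsets and inflated durations, and can drop a Part B exacerbation from the Week 20-72 summary. On the probable intent, to impute only the missing component, what remains is an unnamed anchor. If that anchor is the Part A dose, about 4% of day-missing Part B exacerbation onsets are placed before Part B, under on-schedule visits and uniform onsets.

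The percentages are shares of unresolved partial records, whose number the documents do not give and which is probably small. The treatment phase of adverse events is not affected, and the summaries of exacerbations are exploratory. The point deserves correction because the text is plainly faulty and the remedy is nearly free.

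**What to change.** In SAP 10.7.2.1, for adverse events, exacerbations and concomitant medications, state that only missing components are imputed. If the day is missing, use 01 for a start and the last day of the recorded month for a stop; use January or December only when the month is missing too.

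For adverse events and exacerbations only, state that if the imputed start precedes the first dose of a study part, and the recorded month and year allow onset on or after that dose, the first dose date of that part is used. With the month kept, the two first doses are 20 weeks apart and cannot share a month, so only one can apply. If year-only dates are possible, the text should say which dose takes precedence.

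In SAP 10.4.2, add the partial-date on-treatment default that SAP 10.4.1 has for adverse events.

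Do not extend the first-dose fallback to concomitant medications. They may legitimately start before dosing, and moving them to the first dose would misclassify them under SAP 10.4.3.

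The cost is SAP wording and one edit to the date-imputation program, with no new data. One small downside is that an exacerbation that truly began earlier in the month of the first Part B dose would be counted in Part B, in line with the SAP's worst-case convention.

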10.8. Appendix 8: Population Pharmacokinetic Analyses

10.8.1. Population-PK Analysis

Sparse PK samples collected will be analysed by population PK methods, using appropriate software, and based on the PK population.

Based on mepolizumab PK knowledge, concentrations below the limit of quantification (BLQ) of the assay is considered unlikely at the 100 mg and 40 mg SC dose investigated in view of the PK sampling scheme selected in the study. Thus any such results will be treated as missing in the population PK analysis.

Outlier data will be assessed for plausibility, however the aim is to use all available data whenever possible. Any decision to exclude data will be fully documented and specified in the clinical study report.

The established most recent adult population PK model parameterised in terms of macro-constants (i.e. A, B, alpha, beta) will be used to conduct the analysis of the data from this study.

$$C_i(t) = A_i \cdot \exp(-\text{Alpha} \cdot t) + B_i \cdot \exp(-\text{Beta}_i \cdot t) - (A_i + B_i) \cdot \exp(-K_a \cdot t),$$

Where:

- A denotes the coefficient of the distribution phase
- B denotes the coefficient of the elimination phase
- Alpha denotes the distribution phase rate constant
- Beta denotes the terminal phase rate constant
- pBWT denotes the power for the bodyweight covariate on a parameter
- K_{a_i} absorption rate constant.

Bodyweight will be included as a structural covariate on parameters A, B, Alpha and Beta. In consideration of the sparse sampling used and the relatively small sample size in the study, a number of pharmacokinetic parameters will be fixed from adult values in the model as deemed necessary (e.g. absorption and inter-compartmental rate constant parameters, pBWT).

Individual AUC(0-inf), CL/F, Cmax and t1/2 will be derived as follow:

$$\text{AUC}(0\text{-inf}) = (A/\text{alpha}) + (B/\text{beta}) - (A+B)/K_a$$

$$\text{CL}/F = \text{Dose}/\text{AUC}(0\text{-inf})$$

$$T_{1/2} = \ln(2)/\beta$$

C_{max} will be estimated using an approximation method as described below:

The approximate one compartment solution combining absorption and distribution phases takes the form:

$$C_i'(t) = B*(\exp(-\beta*t) - \exp(-\alpha_2*t))$$

With :

$$\alpha_2 = \alpha + \beta \quad (\text{from the bi-exponential model})$$

Hence

$$T_{max} = \ln((\alpha + \beta)/\alpha)/(\alpha + \beta - \alpha)$$

$$C_{max}(n \text{ doses}) = \sum_{j=1..n} B*(\exp(-\beta*(T_{max} + (j-1)*\tau)) - \exp(-\alpha_2*(T_{max} + (j-1)*\tau)))$$

The parameter estimates from the final PK model, the derived parameters and diagnostic plots assessing the performance of the population PK model will be presented.

Simulation from the final PK model will be conducted and a plot of model predicted (5th, 50th, and 95th Percentiles) mepolizumab plasma concentrations with individual observed plasma concentrations will be presented as a means to validate the final PK Model.

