7.1. Population PK Analysis (Part A)**7.1.1. Overview of Planned Population PK Analysis**

This study is conducted to support the extrapolation of the safety and efficacy data observed in adults in the Phase III Mepolizumab Programme to the paediatric population. To this purpose, one of the PK objectives of the study is to characterize the pharmacokinetics of mepolizumab administered subcutaneously to subjects aged 6 to 11 years old with severe eosinophilic asthma.

A sparse PK sampling scheme has been implemented in this study and the PK samples collected will be analysed by population PK methods, using appropriate software, and based on the PK population defined, unless otherwise specified. All subjects who are in the PK population, i.e. who have at least one measurable PK concentration recorded, will

be included in this analysis. In order to model the paediatric data collected, a number of pharmacokinetic parameters in the model will be fixed using adult values because of the sparse sampling implemented in this paediatric study and the relatively small sample size selected. In particular estimation of absorption and distribution parameters is unlikely to be meaningful based on the proposed sampling scheme.

A description of the key models tested during the model development will be provided and tabulated. The population PK parameter estimates (AUC(0-inf), clearance, C_{max} and t_{1/2}) with 95% CI from the final model will be tabulated (for mepolizumab overall (Mepolizumab SC)). Goodness of fit plots for the final model will be presented.

Additionally, the individual PK parameter estimates (also called model-predicted post-hoc individual PK parameter estimates) for AUC_(0-inf), clearance, C_{max} and t_{1/2} as well as the individual observed and predicted plasma PK concentrations will be listed and summarised by mepolizumab dose and mepolizumab overall using descriptive statistics. The summary of the model-predicted post-hoc individual PK parameter estimates will include summary statistics for untransformed and log_e-transformed data. See details of the summary statistics in Section 10.5.3.

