10.8.2. Additional Analysis to Support Paediatric Extrapolation Strategy

10.8.2.1. Population-PK analysis

In addition, to confirm that paediatric PK data from 6-11 years old subjects can be predicted from the adult PK model, the most recent population PK model will also be applied directly to the dataset without estimation (e.g. maxevals=0 in NONMEM) and predictions generated against which the model will be validated prospectively using appropriate goodness of fit tests. For example the Cramér–von Mises and Kolmogorov–Smirnov tests are accepted methods of comparing Empirical Distribution Functions for model and data (i.e. PK concentrations) to evaluate whether independent observations (observed PK concentrations from the study) are adequately described by a model.

The current PK model consists of a two-compartment pharmacokinetic model with first-order absorption and elimination. Bodyweight is incorporated into the model using allometry with fixed physiological allometric exponents of 0.75 and unity for clearance and volumes, respectively. Albumin and creatinine clearance are also included as covariates of mepolizumab clearance on physiological grounds, however their effects are small and not of clinical relevance.

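### SAP 10.8.1: the printed Tmax is not the peak of the curve it is derived from; coded as printed, three-dose Cmax falls 8-14% below that curve at its correct Tmax

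*SAP*

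**What the plan says.** SAP Section 10.8.1 fits a model with distribution, terminal and absorption rate constants (alpha, beta, Ka). Individual Cmax is then obtained by an approximation rather than from the fitted profile:

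- The approximating curve is introduced with "The approximate one compartment solution combining absorption and distribution phases takes the form" and printed as "C_i'(t) = B*(\exp(-\beta*t) - \exp(-\alpha_2*t))".
- Its fast rate constant is "\alpha_2 = \alpha + \beta \quad (\text{from the bi-exponential model)".
- The slow rate constant is defined: "Beta denotes the terminal phase rate constant".
- Tmax is presented as a consequence of these lines: "T_{max} = \ln((\alpha + \beta)/\alpha)/(\alpha + \beta - \alpha)".
- That Tmax enters the multiple-dose formula, which begins "C_{max}(n \text{ doses}) = \sum_{j=1..n} B*(\exp(-\beta*(T_{max} + (j-1)*\tau))". The number of doses n is not given.

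Cmax is one of the four population-PK parameters in the Part A primary endpoint. Under SAP Section 7.1.1 the individual estimates "will be listed and summarised by mepolizumab dose and mepolizumab overall using descriptive statistics".

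**The concern.** Tmax is stated to follow from the curve, but it does not. Anyone programming the section literally would evaluate the curve before its peak and report that value as the maximum. The error would run in one direction for every child and would affect a primary PK parameter.

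The line defining alpha2 also raises a question. The text says the curve combines absorption with distribution, yet alpha plus beta contains no Ka. Either line, or both, could be misprinted.

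**Working it through.** **Inputs.** Protocol Section 2.2.2 gives a distribution half-life of 1-2 days, a terminal half-life of about 20 days and a median Tmax of 4-8 days after SC dosing. Part A has three doses at 28-day intervals. Hence beta = ln2/20 = 0.0347 per day, and alpha = ln2/1, ln2/1.5 and ln2/2 = 0.693, 0.462 and 0.347 per day. B cancels in every ratio. The SAP prints no numeric Tmax or Cmax to reproduce, so the protocol's 4-8 days is the only benchmark.

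**Algebra.** Setting the derivative of B(e^(-beta t) - e^(-alpha2 t)) to zero gives Tmax = ln(alpha2/beta)/(alpha2 - beta). With alpha2 = alpha + beta this is ln((alpha+beta)/beta)/alpha. The printed line reduces to ln(1+beta/alpha)/beta. The two agree only if alpha = beta.

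**Worked case, distribution half-life 1 day.** alpha2 = 0.7278 per day.
- Printed Tmax = ln(1.05)/0.0347 = 1.41 days. The slope of the single-dose curve there is +0.228 B per day.
- Correct Tmax = ln(21)/0.693 = 4.39 days.
- Three-dose sum at the printed Tmax: 0.952 + 0.361 + 0.137 - 0.359 = 1.091 B.
- Three-dose sum at the correct Tmax: 0.859 + 0.325 + 0.123 - 0.041 = 1.267 B.
- Ratio 1.091/1.267 = 0.861, a shortfall of 13.9%.

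The fast exponential from the two earlier doses is negligible.

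**Across the protocol's range**

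| Distribution half-life (days) | Printed Tmax (days) | Correct Tmax (days) | Ratio, 1 dose | Ratio, 2 doses | Ratio, 3 doses |
|---|---|---|---|---|---|
| 1 | 1.41 | 4.39 | 0.726 | 0.835 | 0.861 |
| 1.5 | 2.09 | 5.76 | 0.756 | 0.866 | 0.892 |
| 2 | 2.75 | 6.92 | 0.781 | 0.891 | 0.918 |

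The shortfall is 8-14% for three doses, 11-17% for two and 22-27% for one. Moving the terminal half-life from 18 to 28 days changes the three-dose figure only to 7.9-14.3%.

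**A bound that does not depend on beta.** Because ln(1+x) < x, the printed Tmax is always below 1/alpha, that is below 1.44-2.89 days. It cannot reach 4 days for any terminal half-life.

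**If alpha2 is the misprinted line.** Choosing alpha2 so that the curve peaks at 4-8 days (0.83 down to 0.31 per day, assumed), the printed Tmax gives a three-dose value 1-25% below that curve at its single-dose peak.

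**Bodyweight sensitivity.** SAP Section 10.8.2.1 uses "fixed physiological allometric exponents of 0.75 and unity for clearance and volumes, respectively" in a different model. If these exponents carry over, both half-lives scale as (W/70)^0.25, with 70 kg an assumed adult reference. The three-dose shortfall is then 9-18% for 15-60 kg.

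**Against the near-peak sample.** Visit 5 is nominally seven days after the third dose. The three-dose curve at day 7 is 1.09-1.10 times the value the SAP would call Cmax. With the visit windows in Protocol Section 4 the gap is 3-11 days and the ratio 0.95-1.17, falling below 1 only after day 9.6-10.7.

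**The case against.** The strongest reply is that this is a slip of symbols. Replacing alpha by beta in the two places where it follows the division sign and the minus sign gives exactly the right formula, and nobody would deliberately write a denominator that adds and subtracts alpha. Symbols can be damaged when a PDF is converted to text, and the code may already be right. This stands as a reason to check the source first and to keep every figure conditional. Against it, beta reads correctly in the curve and in the half-life formula of the same section.

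The second reply is that 8-14% is not the bias of the reported Cmax against the fitted model. That also stands. I ran the full three-exponential model with Ka assumed at 0.15-0.5 per day and a ratio of steady-state to central volume assumed at 1.5-2, keeping cases whose single-dose Tmax is 4-8 days. Cmax at the printed Tmax was 0.68-1.03 of that model's three-dose peak, and at the corrected Tmax 0.74-1.20. The corrected form was closer in most cases but not all, so repairing the closed form does not guarantee an accurate Cmax.

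The third reply is limited reach, and it is largely right. No hypothesis is tested, the adult comparison uses clearance, and fitted profiles are plotted with observed concentrations. The formulas are given for individual estimates; the SAP does not say that they also produce the population Cmax tabulated with its 95% CI. The bodyweight range borrows exponents from another model and is a sensitivity figure only.

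**Conclusion.** The concern holds. As printed, SAP Section 10.8.1 is inconsistent with itself whatever the parameter values. Coded as printed, it would return a three-dose Cmax 8-14% below the SAP's own approximating curve at its correct Tmax.

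The size rests on the adult half-lives in the protocol, on n = 3 and on alpha2 being as printed. It does not measure error against the full model, and the modelling code is not visible. The consequence is confined to Cmax: AUC(0-inf), CL/F, half-life and the adult clearance comparison do not use Tmax, and no adult comparison of Cmax is planned. It should be fixed because a stated rule for a primary PK parameter gives the wrong value when followed.

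**What to change.** 1. Check the alpha2 and Tmax lines against the source SAP and the modelling code, and state the n used for the reported Cmax.
2. If alpha2 = alpha + beta is confirmed, correct Tmax to ln((alpha+beta)/beta)/alpha. This is the single-dose peak; in the three-dose sum it is within 1% of the maximum of the same curve, which falls at 3.8-5.7 days.
3. Preferably, replace the closed form by the numerical maximum of each child's fitted profile, Ka included, over the third dosing interval. This removes the doubt about alpha2 as well.

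The cost is a one-line SAP correction and a code check. If the code follows the printed line, Cmax is recomputed from the existing individual estimates without refitting. If the code is already right, only the text changes.
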